Since each urine sample found to be positive for opiates can be considered to be a treatment failure, up to 51 failures were observable in the 17-week (maintenance) ARC 090 study and up to 48 failures will be observable in the proposed 16-week study. Consequently, the analyses of data from these trials constitute analysis of multiple failures. Many methods to analyze multiple failures have been proposed but the one based on Cox's proportional hazards model by Wei and others (1989) imposes the least restrictive structure on the data and was used to analyze ARC 090 data and is proposed to be used for the multicenter study.

Briefly, this model estimates a regression coefficient between log hazard rate (dependent variable) and the treatment assignment (independent variable) for each failure. Tests of hypotheses to draw inference for each regression coefficient are available. A test of hypothesis to draw inference for a common regression coefficient which is a linear combination of individual regression coefficient is also available. Since the primary interest of the proposed study would be to compare the overall efficacy of the two treatments, the sample size calculations were based on the ability to draw inference for the common regression coefficient.

Since the parameter estimation may be mathematically extremely difficult for a 51- or a 48-dimensional model, the data will be reduced to 16 dimensions by deriving the index of weekly failures described earlier.

In the ARC 090 study, the sample sizes were 53 and 55 for the 8 mg buprenorphine and 20 mg methadone groups, respectively. The estimate of common regression coefficient was found to be 0.348 (p=.015) indicating superiority of buprenorphine over 20 mg methadone treatment. The sample sizes of 120 for each treatment group in the proposed study are more than double of what they were for the ARC 090 study and should provide sufficient cushion against the unexpected. However, the formal sample size/power calculations were still performed using the sample size calculation methods for multiple regression and correlation analyses given in Cohen (1988) using

Table 9.3.2 in this book.

Using Table 9.3.2, the following powers values were obtained for various values of f

f^2	ë	Correlation r	Power
.02	4.8	.14	60%
.15	36.2	.36	99%
.35	84.4	.50	99%

Hence, unless the correlation between treatment assignment and (log) hazard rates is too small, a power of well above 80% should be obtainable. To achieve a power of 80% with N=240, an effect size of about .033 or a correlation of about .18 would be required. This size of correlation amounts to a small to medium size relationship between hazard rates and treatment assignment.

Summary of Assumptions Made in Sample Size Calculations

- 1. One mg dose of buprenorphine will act similar to 20 mg dose of methadone. In other words, if 1 mg dose of buprenorphine happens to be a treatment superior to 20 mg methadone treatment, the expected outcome of the proposed study is likely to be jeopardized.
- 2. Since the proposed study is a 12 center study vis-a-vis ARC 090 study which was a single center study, any unexpected variations across different study centers and deviations from ARC 090 study, e.g., in protocol compliance, collection of urine samples, dropout rates, etc., may render the proposed sample sizes inadequate and thus the expected outcome of the proposed study is likely to be jeopardized.
- 3. The statistical model to be used for analyzing these data assumes proportional hazard rates for the two treatment groups. However, the model is robust to the violation of the proportionality assumption and is probably the most used model to analyze failures. The additional comfort is drawn from the fact that the use of this model for analysis of ARC 090 data did not lead to any unexpected outcomes and proved all clinical expectations to be true.

Interim Monitoring

The study as currently planned consists of a 30-week recruitment period and a 16-week follow-up period. Thus, it would be expected that only one interim report would need to be produced for this study. Because of concerns by NIDA about unblinding of the data prior to the NDA being submitted to the FDA, efficacy data will not be included in the one interim report. That report will

give information on patient recruitment and retention, sample description, data quality and patient safety. If the safety data, however, give an indication of a serious problem that requires the efficacy to be looked at, then analyses of the efficacy data will be performed prior to the final analyses. The decision to review efficacy data in conjunction with a safety problem will be made by the study's Data Monitoring Board.

PATIENT RIGHTS

This protocol will be reviewed by the IRB of the Grantee Organization, Friends Medical Science Research Center, Inc., and the IRB of the VA Cooperative Studies Program. The principal investigators at each performance site will secure approval of the protocol and consent form from their local IRB. Before patients are entered into the protocol, they must sign the informed consent. A sample informed consent can be found in Appendix A.

PARTICIPATION

The study is to be performed at 12 facilities. Each facility will be expected to enter two patients per week for 30 weeks for a total of 60 patients. If each facility recruits its required number of patients, then there would be 720 patients entered into the trial. This is above the 480 patients required for the study as given in the sample size section. These additional projected patients will give some protection against one or two facilities not producing or a larger than expected loss rate. They would also provide increased power for the study results if all facilities do produce and the loss rate is not excessive.

In addition to providing sufficient patients, each facility must also get IRB or R&D Committee (in the case of VA facilities) approval, be able to administer treatment seven days a week and guarantee to follow all aspects of the study protocol. Facilities not functioning properly may be removed from the study.

The following facilities have agreed to participate in this study:

VAMC, Hines, Chicago, IL Milwaukee Co. Mental Health Complex VAMC, West Haven, CT New York ARTC Philadelphia, PA Pizarro Treatment Center, L.A. San Francisco General Hospital VAMC, San Francisco

VAMC, San Juan, PR West L.A. Treatment Program [name].
[name], M.D., Ph.D.
[name]., Ph.D.
[name], M.D., M.P.H.
[name]., Ph.D.
[name].
[name].
[name].

[name]. [name].

VAOPC, Boston VAMC, New York [name]. [name].

REFERENCES AND BIBLIOGRAPHY

Banks CD: Overdose of buprenorphine: Case report. NZ Med J 1979;89:255-256.

Cohen J: Statistical Power Analysis for the Behavioral Sciences (Second Edition). Lawrence Erlbaum Associates, Publishers, Hillsdale, New Jersey, 1988.

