Buprenorphine hydrochloride is classified as a \(\frac{1}{2}\)-opiate partial agonist. It is structurally related to morphine but it has a longer duration of action and its analgesic activity is 25 to 40 times more potent than morphine (Jasinski, Pevnick, Griffith, 1978). The exact mechanism by which buprenorphine produces analgesia is unknown, but it appears to result from a high affinity binding of CNS opiate receptors. Buprenorphine has a high affinity for the \(\frac{1}{2}\)-opiate receptors and dissociates from them slowly, which may contribute to its long duration of action (Jasinski, Pevnick, Griffith, 1978; Jasinski, Fudala, Johnson, 1989). Buprenorphine may appear to act as both an opiate agonist and antagonist; however, this is due to its partial agonist properties, not necessarily the antagonist properties. It produces only a limited maximal effect even when a maximally effective dose is given, so although buprenorphine shows a high affinity for the \(\frac{1}{2}\)-opiate receptor, it has only low to moderate intrinsic activity (Martin, Eades, Thompson, Huppler, Gilbert, 1976).

Buprenorphine is pharmacologically active when given by the subcutaneous, sublingual and oral routes of administration. In 1982, Jasinski et al. reported the onset of action, time to peak, and duration of effect to be similar among the three routes of administration. The relative potency ratio between these three routes of administration has been reported to be 15:10:1, respectively (Lange, Fudala, Dax, Johnson, 1990). When administered sublingually, buprenorphine is readily absorbed with approximately 50% of a dose absorbed systemically (Reckitt and Colman, 1987).

Buprenorphine generally produces few cardiovascular effects. A usual analgesic dose of buprenorphine may depress respiration to the same degree as 10 mg of parenteral morphine sulfate in nonopiate tolerant individuals. The onset of buprenorphine-induced respiratory depression when it does occur is slower than that of morphine-induced respiratory depression and the duration appears to be more prolonged. Like opiate agonists, buprenorphine has been shown to decrease plasma concentrations of luteinizing hormone (LH) and increase plasma concentration of prolactin (Mendelson, Ellingboe, Mello, Kuehnle, 1982). The most common adverse effects reported with the sublingual administration of buprenorphine include drowsiness, dizziness, nausea, and vomiting (Lange, Fudala, Dax, Johnson, 1990).

METHOD

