- 1. *Serum plasma levels of buprenorphine* will be collected at weeks 2 and 8. The sample will be drawn 24 hours after the previous dose and before administration of the next buprenorphine dose. The plasma will be frozen and sent to a central laboratory for analysis.
- 2. *Missed doses* Each site will keep records (Coordinators Weekly Report Form 12 and Dose Administration Record Form 19) documenting the administration of each dose. The number of missed doses will be computed from these records.
- 3. Adverse experiences will be evaluated at screening (Medical History and Status Form 06) and weekly thereafter (Adverse Events Form 16). The questions to elicit this information are open ended. The signs, symptoms or life-events need not necessarily be caused by buprenorphine. The study sites must report within 24 hours serious adverse experiences (i.e., death, experience resulting in permanent disability or hospitalization) to the sponsor (NIDA), the IRB, and the

Clinical Coordinating Center. (The sponsor will report the reaction to FDA.) Form 17 (Serious Adverse Event Form) must be completed for all serious adverse experiences.

- 4. A complete physical examination will be done at baseline and termination and recorded on the medical monitoring form. An abbreviated physical examination (Form 09) will be done monthly. More frequent medical evaluations may be conducted as clinically indicated.
- 5. *The amount of psychosocial treatment* provided patients will be recorded weekly on Form 14 Psychosocial Services Received. This measure is to monitor comparability of groups on the amount of psychosocial services received.

Schedule of Data Collection

Instruments	Screen	Week of Study															
		1	2	3	4	5	6	7	8	9	10	11	12	13	14	15	16
Form 01 - Background Information	X																
Form 02 - Drug Use History	X																
Form 03 - DSM-III-R Criteria for Diagnosis																	
of Opiate Dependence	X																
Form 04 - Global Rating (Staff)	X				X				X				X				X
Form 05 - Global Rating (Patient)	X				X				X				X				X
Form 06 - Medical History and Status	X																
Form 07 - Craving Scale	X																
Form 08 - Laboratory Report	X		X		X				X				X				X
Form 09 - Physical Exam	X				X				X				X				X
Form 10 - Electrocardiogram	X				X												X
Form 11 - Study Admission	X																
Form 12 - Coordinators Weekly Report		X	X	X	X	X	X	X	X	X	X	X	X	X	X	X	X
Form 13 - Weekly Self-Report of Drug Use																	

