and Craving Scale		X	X	X	X	X	X	X	X	X	X	X	X	X	X	X	X
Form 14 - Psychosocial Services Received		X	X	X	X	X	X	X	X	X	X	X	X	X	X	X	X
Form 15 - Concomitant Medication		X	X	X	X	X	X	X	X	X	X	X	X	X	X	X	X
Form 16 - Adverse Events		X	X	X	X	X	X	X	X	X	X	X	X	X	X	X	X
Form 17 - Serious Adverse Events*																	
Form 18 - Termination																	X
Form 19 - Dose Administration Record ?																	
Locator Information	X																
Informed Consent	X																

^{*} To be completed only as necessary.

[?] To be completed daily beginning with the first dose of buprenorphine.

^{6.} *Pregnancy testing* of women of childbearing potential will be done by serum pregnancy test during screening, and monthly. Women of childbearing potential must agree to use adequate contraception while in the study. Should pregnancy occur, her participation in the protocol will be terminated. Results will be recorded on Form 08, Laboratory Report.

^{7.} Laboratory data CBC, UA, SMA-12 (to include BUN, creatinine, SGOT, SGPT, GGT, alkaline

phosphatase and bilirubin, total protein and albumin, and glucose) and EKG will be collected as indicated on the table. These will be performed at each site and the results recorded on Form 08, Laboratory Report, except for the EKG which is recorded on a separate form (Form 10).

Patient Safety Monitoring

The study site physicians, who are blind to buprenorphine dose, will be responsible for the day-to-day clinical monitoring of patients. If the physician observes significant signs or symptoms of buprenorphine toxicity, the physician will order the dispensing nurse to not dispense the patient's buprenorphine dose for that day. If this occurs on three successive occasions, the P.I. will terminate the patient from the study. A patient whose liver enzymes, SGOT and/or SGPT, rise above 8 times the upper limit of normal requires filing of an Adverse Events Form (Form 16) and a Serious Adverse Event Form (Form 17). An immediate telephone report to MDD/NIDA is also required. To remain in the study, such patients must have weekly clinical and laboratory follow-up examinations, more often if necessary, and consultation from a medical specialist in liver disease.

Data Monitoring Board

The group safety data will be monitored monthly by the Study Chairman and periodically reviewed by the Data Monitoring Board.

Psychosocial Treatment Services

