7.3 Clinical Observations

Physical Exams/Vital Signs:

at 12 weeks, 24 weeks, 36 weeks, or whenever termination occurs

The physical exams, performed every third month, may be abbreviated on the clinical judgment of the on-site physician based on the subject's relative good health. More frequent and more thorough examinations will be performed as necessary.

Laboratory Tests: clinical blood chemistries (CBC, SMA-12) and routine

urinalyses: at 12 weeks, 24 weeks, 36 weeks, or whenever

termination occurs

Clinical Measurements: Self report of drug use: weekly

Electrocardiograms: will be performed at 24 weeks after the parent protocol is completed and at

termination

Concomitant medications will be recorded: monthly

Adverse Experiences including Reporting: see original protocol

Pharmacokinetic Measurements:

Although pharmacokinetic studies will not to be performed under this amendment, paired trough plasma samples will be collected whenever a change of dose is planned: a baseline trough sample will be collected just prior to the dose adjustment (and before the subject is actually dosed); and again two weeks thereafter, on the same day of the week as the baseline sample, if possible, another trough sample will be collected. This second trough sample should reflect steady state blood levels. The procedure for collecting steady state blood samples is listed as an amendment to the Parent #999a Protocol:

"Attempt to collect blood as soon as possible after the 14th day of dosing (day 15 would be ideal). Please note, however, that if the subject requires a reinduction during the first two weeks, the 14-day count should re-start with the 1st day of reinduction. Also, do not draw blood on the day after a dose has been missed. The subject must have received dosing for at least three consecutive days prior to drawing blood levels. It is conceivable, that in the case of subjects with many absences, the plasma levels might not be drawn until the fourth week or even later. Similarly, apply the same procedures for the eighth week sample."

"In occasional instances, it may be impossible to collect blood under the conditions and restrictions described above."

Plasma samples should also be collected whenever a significant or serious/unexpected adverse event occurs. These samples should be taken as closely as possible to the event in question.

PLEASE NOTE: Plasma samples will still be sent to the University of Utah.

Urine Collection for Drug Screen Analysis:

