Type of Report I=Anticipated adverse	Relatedness 1=Study drug related 2=Probably study	Severity 1=Mild 2=Moderate	Acti 1=None 2=Prescription or 0	on Taken	Aransy ramina		Outcom	sequelac
event 2 = Unanticipated adverse event 3 = Intercurrent illness 4 = Withdrawal symptom †5 = Development of clinically significant abnormal lab value	drug related 3=Possibly study drug related 4=Unrelated to study drug	lization requi g therapy and equired	zation required *3=Resulted in chronic condition, severe and/or permanent disability quired *4=Deceased the dy due to effect *3=Resulted in chronic condition, severe and/or permanent disability *4=Deceased the dy due to effect					
Considering the patient's lescribe, in the investiga associated information l	tor's own words, eacl	ns 1, 2, and 3 of Adverse Even	above and any oth t, Intercurrent Illu	er pertinen sess or Clir	nt informat nically Sign	ion (i.e., l uificant Ab	ab results normal l	s, etc.), please Lab Value and
Nature of Illnoor Abnormal	ess, Event	Date of Onset (mo day yr)	Date of Resolution (mo day yr)	I. Type of Report	II. Related- ness	III. Severity	IV. Action Taken	V. Outcome
a.							Ш	
ь.				Ш				
c.								
d.						Ш	Ш	
е.						Ш	Ш	
f								
May require completion of								
4. Is a Serious Adverse Event Form (Form 07) required? 1 Yes 2 No								
FORM COMPLETED E	BY							
NVESTIGATOR'S SIG	NATURE			· · · · ·	Date _			
/A Form 10-20923(NR)p November 1991			48					

FORM 07 - S	ERIOUS ADV	ERSE	EVENT FORM	М					
AUDY NO. 999a EXT	CENTER NO.		PATIENT NO.						
	I. ADVERSE	EVENT	STUDY WEEK NO.						
PATIENT INITIALS	2-4. EVENT ONSET Month: Day:	Year:	5. Age: (yrs)						
SEX	7. HEIGHT (in)		8. WEIGHT (lb)						
A. PROVIDE A NARRATIVE DESCRIPTION OF EVENT:									
		ACTION TA	/EN						
B. GREATEST C. STUDY DRUG SEVERITY 1 = Mild 2 = Moderate 3 = Severe 2 = Probable 3 = Severe D. DOSE CHANGE 0 = No Change 0 = No Change 1 = Reduced 0 = No Treatment 1 = Resolved 2 = Temp. Dc'd 1 = Outpatient Tx 2 = Ongoing 3 = Perm. Dc'd 2 = Hospitalization 3 = Died									
G. If Died, List Primary Cause of Death:									
Relevant Tests/Laboratory Data	:								
II. SU	SPECT DRUG(s)	INFORM	IATION						
. Suspect Drug(s) (Give Trade/G	eneric Name(s), Manufa	acturer):							
2. Daily Dose:	3. Route of Administrati	on: 14	14. Dates of Administration: (from/to)						
5. Indication(s) for Use:	16	. Duration of	Administration:						
III. CON	III. CONCOMITANT DRUG(s) AND HISTORY								

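### The 24-hour serious-event rule has no life-threatening criterion, so the protocol text does not require expedited reporting of an overdose or respiratory depression reversed without admission, in either study

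*Combined protocol and SAP*

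**What the plan says.** Item 3 of Other Measures in the parent protocol sets the rule: sites have 24 hours to report "serious adverse experiences (i.e., death, experience resulting in permanent disability or hospitalization". The recipients are the sponsor, the IRB and the Clinical Coordinating Center, and the sponsor then reports to FDA. The same item states that "Form 17 (Serious Adverse Event Form) must be completed for all serious adverse experiences". All other events are collected at screening and "weekly thereafter (Adverse Events Form 16".

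The parent protocol's Patient Safety Monitoring section adds one further trigger. A rise in SGOT or SGPT above 8 times the upper limit of normal needs both the adverse event form and the serious-event form, and "An immediate telephone report to MDD/NIDA is also required".

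The extension keeps this arrangement. Section 7.3 has only "Adverse Experiences including Reporting: see original protocol", and the Synopsis says that parent methods apply unless changed. Extension section 7.1 repeats the liver-test trigger and adds no other.

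**The concern.** The list is introduced as a definition, not as examples, and all three of its items are outcomes. How dangerous an event was while it lasted does not count. An event that threatens life but ends well, without admission, falls outside the list.

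The documents themselves make such an event plausible. The Buprenorphine Pharmacology section describes respiratory depression that starts more slowly than with morphine, and says that "the duration appears to be more prolonged". The extension Synopsis notes that these patients often take other street and prescription drugs, with a greater chance of unexpected interactions. The extension also raises the top dose to 32 mg and introduces doubled weekend doses, under the same reporting rule.

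At stake is how soon those outside the site learn of acute, life-threatening toxicity in a dose-blinded trial meant to support an NDA. The sponsor's own report to FDA depends on hearing from the site.

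**Working it through.** No arithmetic on sample size, power or event rates applies. The check is to take one test event through every expedited trigger in the protocol text, and then follow it through routine reporting.

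**Test event.** Overdose or respiratory depression, immediately life-threatening, reversed in an emergency room or at the clinic, full recovery, no admission. Assumption: hospitalization means admission. The protocol does not define the word.

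| Expedited trigger | Where stated | Met? |
|---|---|---|
| Death | Parent, Other Measures, item 3 | No |
| Permanent disability | Same | No |
| Hospitalization | Same | No |
| Liver enzymes at the 8-times threshold | Parent, Patient Safety Monitoring; extension section 7.1 | No |

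Result: the text requires neither a 24-hour report nor a serious-event form (Form 17 in the parent study, Form 07 in the extension).

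**Other places that deal with toxicity.** In the parent protocol, Patient Safety Monitoring and Termination of Patients From the Study describe withholding doses and ending participation because of toxicity. Neither attaches an expedited report to those steps. Extension section 7.1 likewise covers toxicity without one. Extension section 7.3 asks for a plasma sample when a significant or serious event occurs, but that is an instruction on sampling, not on notification. A laboratory value thus calls for an immediate telephone report, while acute life-threatening toxicity without admission does not.

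**Routine reporting.**

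- Step 1: the event goes on the weekly form. If it happens just after one weekly form is completed, the next is up to 7 days away, against 1 day under the expedited rule: 7 − 1 = 6 days later at most, at this step alone.
- Step 2: under Data Management, completed forms stay at the site until a project monitor has reviewed them, and only then go to the Data Coordinating Center and the NIDA project director. No maximum interval is stated, so the total delay has no upper limit in the documents.
- The IRB and the Clinical Coordinating Center, both 24-hour recipients, are not named as recipients of these routine copies.

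**Extension.** Because section 7.3 refers reporting back to the parent protocol, and section 7.1 adds only the liver trigger, the result is the same. Form 06, question 4, asks whether Form 07 is required, with a yes/no box. The legible coding on that form flags death and chronic, severe or permanent disability, and a broken fragment refers to hospitalization. No life-threatening code can be read.

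**The case against.** The other side has several good points, and most of them limit the consequences.

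- **Sites may still report.** Nothing forbids a voluntary report, and Form 06, question 4, leaves room for judgment. This stands: the gap is in what is required. A reader might infer that such events go unreported; the documents do not support that.
- **The Data Monitoring Board.** A reader might infer that the gap hides these events from the Board. The Board is not a 24-hour recipient; it reviews group safety data periodically, and the Study Chairman monitors them monthly. The rule's wording does not alter what the Board receives within 24 hours.
- **The NDA safety analysis.** A reader might infer that the events would drop out of serious-event counts by dose group. No such count is planned. Secondary Variables compares patients with any medical event and with specific types of event, and extension section 9.0 analyzes adverse events in general. An overdose recorded on the weekly form enters both.
- **Intent.** Form 07 lists "1 = Outpatient Tx" among its treatment codes, which might suggest that non-admitted events were meant to count as serious. The liver-test trigger already explains that code, since it can require the form without admission. The same list also offers mild severity and no treatment, so it looks like a generic code list.
- **How large the risk is.** The pharmacology text compares the degree of respiratory depression with morphine in people who are not opiate tolerant, whereas the trial enrolls daily users. It also describes a limited maximal effect, and extension section 4.0 reports that doses up to 32 mg/day were tolerated in volunteers. So the documents do not support ranking this as the leading acute risk. The point needs only that the event can happen.
- **Unreadable forms.** The parent forms are not in the text available, and parts of extension Form 06, including the note on what triggers Form 07, are broken. Its legible disability code is already somewhat wider than the parent list. Wider printed instructions cannot be excluded, but the protocol text that governs the 24-hour duty contains none.

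**Conclusion.** The gap in the written rule is real. Followed exactly, the protocol text of both studies does not require a 24-hour report, or a serious-event form, for a life-threatening event that ends without death, permanent disability or admission and does not meet the liver trigger. The consequence is later notice to the sponsor, the IRB and the Clinical Coordinating Center: up to 7 days until the weekly form, plus a wait for monitoring that the documents do not bound. The planned adverse event comparisons are not affected.

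This rests on reading hospitalization as admission and on the protocol text alone. The documents give no basis for estimating how many events would be affected. The point is a modest one about a reporting definition, worth acting on because the change is so cheap.

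**What to change.** In item 3 of Other Measures, extend the 24-hour list to life-threatening events, including overdose or respiratory depression that needs emergency treatment, whether or not the patient is admitted. Form 17 then follows automatically, because it is tied to the same definition. Put the same wording in extension section 7.3 and in the instructions for Form 06, question 4, so that the yes/no box is answered against a stated criterion. If the forms already carry a wider criterion, align the protocol text with it.

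The cost is one line of protocol text, matching form instructions and a few more expedited reports. Dosing, treatment, termination rules and the planned analyses are unchanged.
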